### **2.7.5. Partial PFS2 event date**

If year or month is missing, no imputation will be applied. If year and month of progression date on subsequent Antimyeloma therapy are available and day is missing, please impute the day as 15, except,

1. If the Month & Year of Date of progression is the same as the Month & Year of the start date of first line, then the day is imputed as the day of the start date of first line.
2. If the Month & Year of Date of progression is the same as the Month & Year of start date of second line, then the day is imputed as minimum (15, (start day of the second line)).

### **3. INTERIM ANALYSIS AND DATA MONITORING COMMITTEE REVIEW**

There will be one interim analysis for futility which will occur when approximately 60% of the PFS events (99) have occurred. This is expected to occur approximately 8 months after the last subject has been randomized. The purpose of this interim analysis is to evaluate cumulative interim safety and efficacy data. The non-binding futility boundary at this interim analysis will be determined using the Kim-DeMets power spending function with parameter  $p=4.0$ . The beta spent at this analysis will be 0.0194.

### **4. SUBJECT INFORMATION**

Analyses of subject disposition, demographic and baseline disease characteristics will be conducted on ITT analysis set. Analyses on extent of exposure will be conducted on safety analysis set. No statistical comparisons between the two treatment groups will be performed.

#### **4.1. Demographics and Baseline Characteristics**

The following subject demographics will be summarized using descriptive statistics:

- Age (continuous)
- Age category (< 65 years, 65 to < 75 years, and  $\geq 75$  years)
- Sex (male, female)
- Race (White, non-white)
- Ethnicity (Hispanic or Latino, Not Hispanic or Latino)
- Height (cm)
- Weight (kg) (< 45kg,  $\leq 65$  kg,  $> 65$  kg to 85 kg,  $> 85$  kg, and  $> 120$  kg)
- Baseline ECOG performance status (0, 1, >1)

The following baseline disease characteristics will be summarized using descriptive statistics:

- Type of myeloma by immunofixation or serum FLC assay (IgA, IgD, IgE, IgG, IgM, light chain, biclonal, or negative immunofixation)
- Type of measurable disease
- Plasma cell percentage by bone marrow aspirate or biopsy (< 10, 10 - < 20, 20 - < 40, 40 - < 60,  $\geq 60$ )
- Focal lesions
- Serum M-protein
- Serum FLC ratio
- Time from first evidence of MGUS to randomization (years)
- Time since initial diagnosis of SMM to randomization (years)
- Cytogenetic abnormality
- Renal function
- Hepatic function
- Mayo 2018 risk criteria
- ISS stage

In addition, a descriptive summary of selected hematology and chemistry laboratory analytes at baseline will be provided for each treatment group and overall. The baseline toxicity grade of selected laboratory analyte in hematology and chemistry panel will be summarized by treatment group using frequency. Central laboratory results will be used for this purpose whenever possible.

A summary of stratification factors used in the randomization (number of risk factors associated with progression to multiple myeloma) based on IWRS will be provided to evaluate whether randomization process was appropriately executed in the study.

## **4.2. Disposition Information**

The number of subjects who enrolled, treated, and discontinued treatment with reasons of discontinuation reported on eCRF will be summarized. The number of subjects who discontinued from study with the reported reasons will also be presented.

Subject enrollment will also be summarized by country and site for intent-to-treat analysis set.

- A listing of subjects who discontinued study treatment including reasons for discontinuation will be provided. A similar listing will be provided for subjects who discontinued study participation.

## **4.3. Medical History**

General medical history will be summarized by body system organ class and preferred term for each treatment group and overall.

## **4.4. Extent of Exposure**

Extent of exposure to study drug will be summarized and presented on safety analysis set.

Treatment duration and the total number of treatment cycles will be summarized descriptively. The number and percentage of subjects treated within each cycle will also be summarized for the dara-SC subjects.

Treatment duration in months is derived as last non-zero daratumumab dosing date – first non-zero daratumumab dosing date + 1 and then divided by 365.25/12. The maximum number of treatment cycles for each subject is the largest cycle number in which a subject receives any non-zero dose of daratumumab.

Total dose (mg) for Dara group is defined as the sum of total dose (mg) administered and recorded on CRF at each visit. Descriptive statistics for the total daratumumab dose received and total number of injections will be provided.

Dose intensity, which is defined as the sum of total dose administered in all cycles divided by the number of treatment cycles, will be calculated and summarized for daratumumab treatment

group. Additionally, the daratumumab dose intensity will be summarized by Cycle during the treatment.

Relative dose intensity (%), which is defined as the ratio of total dose received and total planned dose (calculated as the planned dose level times the number of administered injections), will be calculated and summarized for each treatment group. Additionally, the relative dose intensity will be summarized by Cycle during the treatment.

The incidences of dose delays and corresponding reasons will be provided. The frequencies of actions planned prior to injection start and taken during injection will be summarized, together with reasons reported on eCRF. In addition, a summary of dose delays will also be provided by cycle during the treatment.

The treatment label identifier dispensed by each subject will be listed.

A separate listing including all daratumumab injection data will also be provided.

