6.4.2. Infusion-related Reactions

Subjects should be observed carefully during study drug administrations. Trained study staff at the clinic should be prepared to intervene in case of any IRRs, and resources necessary for resuscitation (eg, agents such as epinephrine and aerosolized bronchodilator, also medical equipment such as oxygen tanks, tracheostomy equipment, and a defibrillator) must be available at the bedside.

If an IRR develops, then daratumumab administration should be temporarily interrupted. Please see the IPPI for further details. Subjects who experience adverse events during daratumumab

administration must be treated for their symptoms. Subjects should be treated with acetaminophen, antihistamine, or corticosteroids, as needed. Intravenous saline may be indicated. For bronchospasm, urticaria, or dyspnea, subjects may require antihistamines, oxygen, corticosteroids, or bronchodilators. For hypotension, subjects may require vasopressors. In the event of a life-threatening IRR (which may include pulmonary or cardiac events) or anaphylactic reaction, daratumumab should be discontinued and no additional daratumumab should be administered to the subject.

Infusion-related Reactions of Grade 1 or Grade 2

If the investigator assesses a Grade 1-2 IRR adverse event to be related to administration of study drug, then the daratumumab administration should be paused. When the subject's condition is stable, daratumumab administration may be restarted at the investigator's discretion.

If the subject experiences a Grade 2 or higher event of laryngeal edema, or a Grade 2 or higher event of bronchospasm that does not respond to systemic therapy and does not resolve within 6 hours from onset, then the subject must be withdrawn from daratumumab treatment.

Infusion-related Reactions of Grade 3 or Higher

For IRR adverse events (other than laryngeal edema or bronchospasm) that are Grade 3, the daratumumab administration must be stopped and the subject must be observed carefully until resolution of the adverse event or until the intensity of the event decreases to Grade 1, at which point the daratumumab administration may be restarted at the investigator's discretion. If the intensity of the adverse event returns to Grade 3 after restart of the daratumumab administration, then the subject must be withdrawn from daratumumab treatment.

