6.5. Dose Delays and Dose Modification

6.5.1. Dose Modification

Dose modification of daratumumab (increase or decrease) is not permitted. Dose delay is the primary method for managing daratumumab-related toxicities. On the first day of each new treatment cycle and before each dose of daratumumab, the subject will be evaluated by the treating physician for possible toxicities that may have occurred after the previous dose(s). Toxicities are to be assessed according to NCI-CTCAE, Version 4.03. Cycle delays will be based on the toxicity experienced during the previous cycle of therapy or newly encountered on Day 1 of a cycle.

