6.5.2. Toxicity Management

Daratumumab must be held if any of the following criteria are met, to allow for recovery from toxicity, regardless of relationship to study drug:

- Grade 4 hematologic toxicity, except for Grade 4 lymphopenia
- Grade 3 or higher thrombocytopenia
- Febrile neutropenia
- Neutropenia with infection, of any grade
- Grade 3 or higher non-hematologic toxicities with the following exceptions:
 - Grade 3 nausea that responds to antiemetic treatment within 7 days
 - Grade 3 vomiting that responds to antiemetic treatment within 7 days
 - Grade 3 diarrhea that responds to antidiarrheal treatment within 7 days
 - Grade 3 fatigue that was present at baseline or that lasts for <7 days after the last administration of daratumumab
 - Grade 3 asthenia that was present at baseline or that lasts for <7 days after the last administration of daratumumab

Daratumumab administration should be resumed when the toxicity has resolved to Grade 2.

Dose delays affecting Day 1: If Day 1 of a cycle is delayed, the entire cycle will be delayed until either the dose can be given or daratumumab is to be discontinued (see below). If the start of a cycle is delayed, the starting day of subsequent cycles is adjusted accordingly.

Dose delays affecting days other than Day 1: If an administration does not commence within the prespecified window ([Table 7](#)) of the scheduled administration date, then the dose will be considered a missed dose. Administration may resume at the next planned dosing date. A missed dose will not be made up.

Table 7: Daratumumab Administration Schedule for Within Cycle Doses

Cycles	Frequency	Dose Held	Dosing Restart
1 and 2	Weekly	>3 days	Next planned weekly dosing date
3 to 6	Every 2 weeks	>1 week	Next planned biweekly dosing date

Any adverse event deemed to be related to daratumumab that requires a dose hold of >28 days due will result in permanent discontinuation of daratumumab. If a dose delay occurs, then PK and pharmacodynamic assessments should be performed on the actual day of study drug administration, not on the original scheduled administration day.

In case the dose is to be delayed because of reasons other than toxicity, the aforementioned rules should be applied as well (refer to [Section 6](#)). However, every effort should be made to avoid dose

delays because of reasons other than toxicity (refer to Section [6.5.3](#) for details on interrupted or missed doses).

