6.5.3. Interruption or Missed Doses

A daratumumab dose held for more than 3 days from the per-protocol administration date for any reason other than toxicities suspected to be related to daratumumab should be brought to the attention of the sponsor at the earliest possible time. Subjects missing ≥ 3 consecutive planned doses of daratumumab for reasons other than daratumumab-related toxicity should be withdrawn from treatment, unless, upon consultation with the sponsor and the review of safety and efficacy, continuation is agreed upon.

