#### **Daratumumab 1800 mg SC (for daratumumab arm):**

- Cycles 1 and 2: Days 1, 8, 15, and 22 (QW)
- Cycle 3 to 6: Days 1 and 15 (Q2W)
- Cycles 7 to 39: Day 1 (Q4W)

Dose modification of daratumumab (increase or decrease) is not permitted. Dose delay is the primary method for managing daratumumab-related toxicities. Protocol-specified dose delays for daratumumab will be adjusted as necessary according to the treatment guidelines. Daratumumab may be delayed for up to 3 days, 7 days or 14 days during Cycles 1 and 2, Cycles 3 to 6 and Cycles 7+, respectively, to allow for recovery from toxicity. If daratumumab administration does not commence within the prespecified window of the scheduled administration date, then the dose will be considered a missed dose. A missed dose will not be made up. Doses of daratumumab in Cycles

7+ may be delayed up to 4 weeks. If a dose is delayed, then the dates of all subsequent doses must be adjusted. Any adverse event deemed to be related to daratumumab that requires a dose hold of more than 28 days will result in permanent discontinuation of daratumumab. Subjects missing 3 or more consecutive planned doses of daratumumab for reasons other than toxicity should be withdrawn from treatment, unless, upon consultation with the sponsor and the review of safety and efficacy, continuation is agreed upon. Subjects in daratumumab treatment group will be treated until disease progression, unacceptable toxicity, or other reasons as listed in Section 10.2 of protocol.

This study will use the IMWG consensus recommendations for MM treatment response criteria (Durie 2007, Rajkumar 2011, Kumar 2016). For quantitative immunoglobulin (QIg) at baseline, M-protein, and immunofixation measurements in serum and 24-hour urine, the investigator will use results provided by the central laboratory. Disease progression will be measured according to the published international uniform diagnostic criteria for MM established by the IMWG (Rajkumar 2014). Progression evaluations for the primary endpoint/final analysis will be based on IRC review, in a blinded fashion, to objectively and consistently implement the IMWG diagnostic criteria for MM.

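### The SAP's relative dose intensity divides by injections actually given, so it stays at about 100% however many injections are missed (minor)

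*SAP*

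**What the plan says.** SAP 4.4 (Extent of Exposure) takes the milligrams recorded on the CRF as the dose received and divides them by "total planned dose (calculated as the planned dose level times the number of administered injections"). The result is to be summarised overall and by cycle, for each treatment group.

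The same section defines an absolute dose intensity, the total milligrams divided by the number of treatment cycles, and adds that "the daratumumab dose intensity will be summarized by Cycle during the treatment". It also plans total dose, number of injections, subjects treated within each cycle, dose delays with reasons and a listing of all injection data. On actions around the injection it says: "The frequencies of actions planned prior to injection start and taken during injection will be summarized".

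Three Protocol rules bear on how the ratio behaves:

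- Section 6.5.1: "Dose modification of daratumumab (increase or decrease) is not permitted".
- Section 6.4.2: "If an IRR develops, then daratumumab administration should be temporarily interrupted".
- Section 6.5.2: a within-cycle dose outside its window is missed and is not made up, whereas for the first day of a cycle "If Day 1 of a cycle is delayed, the entire cycle will be delayed until either the dose can be given".

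**The concern.** A relative dose intensity is normally read as the share of the intended regimen that the subject received. Here the denominator carries the name of planned dose but counts only injections that took place. With a fixed dose per injection, omitting an injection removes the same 1800 mg from top and bottom. A table of values near 100% would then suggest near-complete adherence to the schedule, whatever the number of omissions.

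The loss is confined to the exposure description. The primary comparison, the hierarchical tests and the interim futility rule do not use this statistic. What is missing is an overall, subject-level percentage of schedule delivered, which a reader would want beside the safety and efficacy results of a treatment lasting up to 39 cycles.

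The measure is also to be reported for each treatment group. The active-monitoring arm receives no study drug (Protocol 6), so there it is zero over zero.

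**Working it through.** The documents state no relative dose intensity figure, so there is none to reproduce. The check applies the stated formula to the stated schedule.

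**Inputs** (SAP 1.2; Protocol 6.2 and 6.5.1)
- Dose per injection: 1800 mg, not modifiable.
- Injections per cycle: 4 in Cycles 1–2, 2 in Cycles 3–6, 1 in Cycles 7–39.
- Scheduled over 39 cycles: 2×4 + 4×2 + 33×1 = 49, or 49×1800 = 88,200 mg.
- Planned milligrams per cycle: 7200, 3600 and 1800 respectively.

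**Formulas**, with S injections scheduled and k wholly missed, all others complete:
- SAP ratio = 1800(S−k) / [1800(S−k)] = 100% for every k.
- Share of schedule = (S−k)/S.
- Overall dose intensity = 1800(S−k) / cycles.

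The documents give no rate of missed injections, so the values of k are illustrative assumptions.

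| Course | Given / scheduled | SAP ratio | Share of schedule | Overall mg per cycle |
|---|---|---|---|---|
| Cycles 1–2, 4 missed | 4/8 | 100% | 50% | 7200/2 = 3600 |
| Cycles 1–6, none missed | 16/16 | 100% | 100% | 28,800/6 = 4800 |
| Cycles 1–6, 5 missed | 11/16 | 100% | 68.8% | 19,800/6 = 3300 |
| Cycles 1–6, 8 missed | 8/16 | 100% | 50% | 14,400/6 = 2400 |
| 39 cycles, none missed | 49/49 | 100% | 100% | 88,200/39 = 2262 |
| 39 cycles, 5 missed | 44/49 | 100% | 89.8% | 79,200/39 = 2031 |
| 39 cycles, 8 missed | 41/49 | 100% | 83.7% | 73,800/39 = 1892 |
| 39 cycles, 10 missed | 39/49 | 100% | 79.6% | 70,200/39 = 1800 |

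**How far k can go.** On the Protocol 6.5.2 reading, a delayed Day 1 moves the cycle, so only the other injections can be missed: 2×3 + 4×1 = 10. With every Day 1 given, the most that can be missed without three in a row is 2 + 2 + 4 = 8. Missing all 10 means three in a row in both Cycle 1 and Cycle 2. Under Protocol 6.5.3, subjects missing three or more "consecutive planned doses of daratumumab for reasons other than daratumumab-related toxicity should be withdrawn from treatment, unless, upon consultation with the sponsor", continuation is agreed.

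**What does move the SAP ratio.** One half-delivered injection among 49 gives 48.5/49 = 98.98%. Add five wholly missed injections and the SAP ratio is 43.5/44 = 98.86%, while the share of schedule is 43.5/49 = 88.78%.

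**Why overall mg per cycle is no substitute.** The schedule is front-loaded, so this figure depends on time on treatment. A subject who stops after Cycle 6 with half the schedule missed has 2400 mg per cycle, above the 2262 of a 39-cycle completer who missed nothing. The like-for-like value at six cycles with nothing missed is 4800.

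**The case against.** The strongest reply is that this is mostly a matter of naming. The SAP states its denominator openly, nothing else in the plan depends on it, and missed injections can be seen in several other places. By-cycle milligrams show them directly against 7200, 3600 and 1800 mg. Injection counts, subjects treated per cycle, delays and the listing add to this; SAP 6.1.7 tabulates adverse events leading to a skipped dose, and SAP 4.5 tabulates major deviations for an incorrect dose. The overall percentage could be derived from data already planned.

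The ratio also carries some information of its own. With a non-modifiable dose, it picks up injections interrupted for a reaction: if one of four in Cycle 1 is half delivered, that cycle scores 3.5/4 = 87.5%. Finally, the replacement gains little by cycle. On the Protocol 6.5.2 reading it too is about 100% in Cycles 7–39, and in Cycles 1–6 it repeats the mg-per-cycle rows.

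All of this is right, and it is why the point is minor. It does not rescue the definition. The quantity labelled planned dose is not the planned dose, and no planned summary gives the overall percentage that the label promises.

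**Conclusion.** The concern holds, as a minor one. As written, the ratio is 100% for any number of wholly missed injections when those given are complete, and about 100% when a few are partial. Against the schedule, the corresponding shares are 89.8% with 5 of 49 missed, 83.7% with 8 of 49, and 50% with 4 of 8 missed in Cycles 1–2. These counts are assumptions that show the size of the gap; they do not predict what happened in the trial. The figure of 8 as the most that can be missed without three in a row also assumes the Protocol 6.5.2 reading, under which a delayed Day 1 is shifted and not missed. No efficacy result, significance level or decision rule is affected.

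**What to change.** In SAP 4.4, define total planned dose as the protocol dose level times the injections scheduled in cycles started up to treatment discontinuation: 4 per cycle in Cycles 1–2, 2 in Cycles 3–6 and 1 from Cycle 7. In the last cycle, count only those due by discontinuation. Apply this overall and by cycle, for the daratumumab arm only. If the present ratio is kept, give it a name such as proportion of dose delivered per injection. State that cycle delay appears only in the dose-delay summary, since the revised measure does not capture it. The real addition is the overall percentage.

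One conflict must be settled before scheduled injections can be counted. Protocol 6.5.2 shifts the whole cycle when Day 1 is delayed and applies the missed-dose window to other days only. SAP 1.2 sets a window for each part of the schedule ("may be delayed for up to 3 days, 7 days or 14 days during Cycles 1 and 2, Cycles 3 to 6"; the 14-day figure is for later cycles), exempts Day 1 in no cycle, treats a dose outside its window as missed, and then allows a delay of up to 4 weeks from Cycle 7. These passages must be reconciled; this review does not say which rule should govern.

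Apart from that reconciliation, the cost is SAP wording and a small derivation change, as the injection data are already in the eCRF. Protocol Amendment 6 says the primary analysis has concluded, so if exposure tables have been issued this becomes a supplementary re-derivation. The reported percentage will look less favourable.

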#### **4.5. Protocol Deviations**

Major protocol deviations will be summarized for ITT analysis set by the following types of deviation for each treatment group:

- Entered but did not satisfy inclusion/exclusion criteria
- Developed withdrawal criteria but not withdrawn
- Received wrong treatment or incorrect dose
- Received an excluded concomitant treatment
- Other

COVID-19 related major protocol deviations will be included in the summary as well. A list of subjects with major protocol deviations including subject ID, type of deviation, and reasons for deviation will be provided.

#### **4.6. Prior and Concomitant Medications**

Medications administered prior to the first dose date of study drug will be considered as prior medications. Concomitant medications are defined as those medications taken on or after the first dose date through 30 days after the last dose date, or the start date of subsequent therapy, whichever occurred first.

Prior medications will be summarized on ITT analysis set by therapeutic class, pharmacologic class, and preferred term.

Concomitant medications will be summarized on safety analysis set by therapeutic class, pharmacologic class, and preferred term.

Pre-injection medications and post-injection medications will also be summarized, respectively. Pre-injection medications will be grouped by therapeutic class, pharmacologic class, and Drug. The incidence of pre-injection medications will be presented by the aforementioned groups and preferred terms. The similar summary will be provided for post-injection medications.

